Any disease in the decompensation stage;
Neuralgic and psychological disorders that interfere with the study;
Cancer;
Non-transportable patients;
Patients who do not reside in Almaty;
Patients who have refused to participate in the study.

Examined for eligibility - 76 people;

Confirmed eligible - 60 people. According to our strict exclusion criteria, we had to remove 16 people [8 – oncological patients, 5 – moved house, 3 patients refused to participate];

Included in the study - 60 patients;

Completing follow-up and analysed - 60 patients.

Statistical Analysis Plan

Gut microbiota:

IBM SPSS ver. 23.0 (Chicago, IL, USA) was used to determine the statistical significance of the obtained data. All the indicators were verified for compliance with the law on normal distribution. If the variables obeyed this law, the Student's paired t-test was applied to determine statistical significance between the values before and after milk intake. Otherwise, the Wilcoxon sign rank criterion was used.

A single-factor analysis of variance was employed to verify the effect of administering freeze-dried mare's milk, which could potentially affect the indicators of gut microbiota.

Antiphospholipid antibodies:

The 95% confidence interval for aPL value was calculated for both median and mean. The confidence interval for the latter one was calculated in the descriptive statistics menu in IBM SPSS ver. 23.0 (Chicago, IL, USA).

It is necessary to find the value of the confidence coefficient (Student's criterion (t)) in the table of critical t-values, considering the total number of respondents (n) to find out a confidence interval for the median with a given confidence probability (p). After that, the calculation of the natural integer number (C) is needed for such a probability value: $C_p = (n/2 - t(p) \sqrt{n}/2)$. The lower confidence limit for the median is $X (C_p)$, where X is the ordinal number of the value in the ranked variation series corresponding to the lower boundary of the confidence interval. The upper confidence limit for the median is $X (n + 1 - C_p)$, where X is the ordinal number of the value in

the ranked variation series corresponding to the upper boundary of the confidence interval.

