If the normal distribution law is followed, the Student's paired t-test was used to determine statistical significance between values before and after freeze-dried mare's milk. If not, the Wilcoxon sign rank criterion was used for intergroup comparison. One-way analysis of variance (ANOVA) was used to determine the relationship between the mare's milk prescription factor and aPL levels in both groups.

Quality of life:

IBM SPSS ver. 23.0 (Chicago, IL, USA) was used to determine the statistical significance of the obtained data. All the indicators were verified for compliance with the law on normal distribution. If the variables obeyed this law, the Student's paired t-test was applied to determine statistical significance between the values before and after milk intake. Otherwise, the Wilcoxon sign rank criterion was used.

A single-factor analysis of variance was employed to verify the effect of administering freeze-dried mare's milk, which could potentially affect the quality-of-life scores.

Results section

Gut microbiota analysis.

In the main group, after taking freeze-dried mare's milk, there was a decrease in the content of bacteria phyla Bacteroidetes, Proteobacteria, Verrucomicrobia and Chloroflexi (by 3.03%, 2.83%, 0.47% and 0.16, respectively), and an increase in the content of bacteria phyla Nitrospirae, Tenericutes, Cyanobacteria, Spirochaetes, Euryarchaeota, Actinobacteria and Firmicutes (by 0.02 %, 0.05%, 0.15%, 0.17%, 0.24%, 1.42% and 7.62%, respectively).

The Fusobacteria phylum was absent according to the results of mare's milk intake in all respondents. The Elusimicrobia phylum, on the contrary, was present in some respondents as a result of therapy.

Attention is also drawn to the presence of the Synergistetes phylum, which was absent in the control group both before and after therapy. Moreover, the difference between the Firmicutes, Proteobacteria, Chloroflexi, Cyanobacteria and Synergistetes phyla was statistically significant (Table 1).

Table 1. The percentage terms of all phyla of the gut microbiota in the main group before and after taking freeze-dried mare's milk (CI - confidence interval).

Phylum name	Before	After	95% CI (t-student)	p (t-student)
Bacteroidetes	32,32%	29,43%	-0,01; 0,07	0,178
Firmicutes	45,31%	51,87%	-0,09; -0,02	0,001
Proteobacteria	9,25%	6,52%	0,1; 0,28	<0,001
Actinobacteria	3,75%	4,9%	-0,15; 0,14	0,951
Euryarchaeota	1,28%	1,52%	-0,42; 0,1	0,204
Verrucomicrobia	1,29%	0,83%	-0,09; 0,32	0,223

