Chloroflexi	0,23%	0,07%	0,04; 0,28	0,011
Cyanobacteria	0,16%	0,31%	-1,95; -0,17	0,028
Spirochaetes	0,08%	0,25%	-0,51; 0,17	0,324
Nitrospirae	0,01%	0,03%	-0,07; 0,02	0,235
Tenericutes	0,04%	0,09%	-0,2; 0,01	0,491
Fusobacteria	0,07%	0,00%	-0,05; 0,2	0,247
Elusimicrobia	0,00%	0,11%	-0,24; 0,02	0,109

Synergistetes	0,01%	0,09%	-0,14; -0,02	0,009
---------------	-------	-------	--------------	-------

In the control group, after taking freeze-dried mare's milk, there was a decrease in the content of bacteria phyla Bacteroidetes, Firmicutes, Chloroflexi and Cyanobacteria (by 2.5%, 0.4%, 0.07% and 0.07%, respectively), and an increase in the content of bacteria phyla Spirochaetes, Tenericutes, Fusobacteria, Verrucomicrobia, Proteobacteria, Euryarchaeota and Actinobacteria (by 0.005%, 0.01%, 0.04%, 0.24%, 0.26%, 0.48% and 3.56%, respectively).

The Nitrospirae and Elusimicrobia phyla were absent as a result of taking mare's milk in all respondents of the control group. At the beginning of therapy, some respondents were found to have bacteria of the Caldithrix phylum, which were absent during the repeated measurement. The Thermotogae phylum was found in several members of the control group during two measurements.

Moreover, the difference between the Actinobacteria and Chloroflexi phyla in the control group was statistically significant (Table 2).

Table 2. The percentage terms of all phyla of the gut microbiota in the control group after 2 stool tests (CI - confidence interval).

Phylum name	First test	Second test	95% CI (t-student)	p (t-student)
Bacteroidetes	32,27%	29,77%	-0,06; 0,08	0,754
Firmicutes	46,5%	46,1%	-0,06; 0,07	0,899
Proteobacteria	7,65%	7,91%	-0,1; 0,12	0,823
Actinobacteria	5,8%	9,36%	-0,46; -0,1	0,003
Euryarchaeota	0,39%	0,87%	-0,74; 0,24	0,209
Verrucomicrobia	1,72%	1,96%	-0,97; 0,85	0,871
Chloroflexi	0,10%	0,03%	0,002; 0,15	0,044
Cyanobacteria	0,41%	0,34%	-1,42; 1,89	0,728
Spirochaetes	0,007%	0,012%	-0,01; 0,004	0,324
Nitrospirae	0,01%	0,00%	-0,01; 0,02	0,324
Tenericutes	0,04%	0,05%	-0,12; 0,1	0,857
Fusobacteria	0,01%	0,05%	-0,13; 0,05	0,357
Elusimicrobia	0,03%	0,00%	-0,01; 0,07	0,090
Caldithrix	0,02%	0,00%	-0,01; 0,03	0,160
Thermotogae	0,02%	0,01%	-0,03; 0,06	0,454

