The proportion of Bacteroidetes and Firmicutes in the gut microbiota is most significant. Summarizing their values in the main and control groups, we can see that their content increased in the former and decreased in the latter. Statistical analysis revealed a significant difference in the content of these phyla between the main group compared to the control group (Table 3).

Table 3. The percentage terms of Bacteroidetes and Firmicutes phylum in the main and control groups.

Main group			Control group		
Bacteroidete s+Firmicutes (before)	Bacteroidetes +Firmicutes (after)	p (Wilcoxon)	Bacteroidete s+Firmicutes (first test)	Bacteroidetes +Firmicutes (second test)	p (Wilcoxon)
77,63%	81,3%	0,026	78,76%	75,87%	0,213

To determine the effect of freeze-dried mare's milk on the gut microbiota at the phylum level, a one-factor analysis of variance was performed. A statistically significant relationship between such a factor as the administration of freeze-dried mare's milk was revealed in the Firmicutes, Elusimicrobia and Proteobacteria phyla (Table 4).

Table 4. The relationship between the use of prescribed freeze-dried mare's milk and indicators of gut microbiota at the phylum level.

Phylum name	p (One-way ANOVA)
Bacteroidetes	0,180
Firmicutes	0,048
Proteobacteria	0,043
Actinobacteria	0,186
Euryaychaeota	0,403
Verrucomicrobia	0,583
Chloroflexi	0,220
Cyanobacteria	0,280
Spirochaetes	0,340
Nitrospirae	0,143
Tenericutes	0,657
Fusobacteria	0,140
Elusimicrobia	0,044
Bacteroidetes + Firmicutes	0,037

Overall, the intake of freeze-dried mare's milk by post-COVID patients primarily contributed to an increase in the content of the sum of two major phyla of gut microbiota — Bacteroides and Firmicutes, with the latter being particularly significant. There is also a notable decrease in the number of bacteria from the Proteobacteria phylum in the main group, which includes representatives of pathogenic microflora.

Antiphospholipid antibody analysis.

29 out of 30 main group patients (96.67%) had normal IgM and IgG levels before taking freeze-dried mare's milk. In the case of the control group, aPL levels were normal in all respondents. The aPL levels were normal in patients of both groups after the second ELISA (Table 5).

Table 5. Antiphospholipid antibody scores of each patient in the main and control groups after two assays (aPL -antiphospholipid antibodies).

Main group		Control group					
aPL (before)		aPL (after)		aPL (first assay)		aPL (second assay)	

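### Tables 1 and 2 print confidence intervals with no unit and on more than one scale, so ten of the 29 exclude the percentage-point change in their own row

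*Combined protocol and SAP*

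**What the plan says.** The gut microbiota part of the Statistical Analysis Plan checks each indicator for normality and then names the test: "If the variables obeyed this law, the Student's paired t-test was applied to determine statistical significance between the values before and after milk intake". The fallback is a Wilcoxon test. No transformation is mentioned, and no unit is given for the change.

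In the Results section, Table 1 is captioned "The percentage terms of all phyla of the gut microbiota in the main group before and after taking freeze-dried" mare's milk and Table 2 "The percentage terms of all phyla of the gut microbiota in the control group after 2 stool tests". Both print the two mean shares with a percent sign. The interval column in each is headed only "95% CI (t-student"), and its entries carry no unit. The text above each table gives the changes as percentages. The patient flow list states "Completing follow-up and analysed - 60 patients", and the enrolment entry gives 30 patients per group.

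The closing text of the gut section relies on two of the affected phyla, Firmicutes and Proteobacteria. Of the latter it says "There is also a notable decrease in the number of bacteria from the Proteobacteria phylum in the main group".

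**The concern.** A paired-t interval is symmetric about the mean of the individual differences, and that mean equals the difference between the two printed means when everyone contributes both readings. If the interval excludes that difference, it belongs to another quantity, or one of the figures is wrong.

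A reader who takes Table 1 at face value sees a 6.56-point rise in Firmicutes beside an interval running from 0.02 to 0.09. The text therefore quotes one quantity, while the interval and its p-value appear to describe another that is never named. Effect size and precision for the main microbiome findings cannot be recovered, and rows within one column cannot be compared.

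**Working it through.** **Inputs.** First mean, second mean, interval and p-value for the 14 rows of Table 1 and the 15 rows of Table 2; n = 30 per group, so 29 degrees of freedom.

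**Formulas.** Change d = first mean − second mean, in percentage points. Midpoint m = (lower + upper)/2. If the interval is in points, m should equal d within rounding: 0.01 on d plus 0.005 on m for figures printed to two decimals.

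**Rows in percentage points.** Main-group d and m: Chloroflexi 0.16 and 0.16; Spirochaetes −0.17 and −0.17; Elusimicrobia −0.11 and −0.11; Synergistetes −0.08 and −0.08; Fusobacteria 0.07 and 0.075. Control: Fusobacteria −0.04 and −0.04; Elusimicrobia 0.03 and 0.03; Chloroflexi 0.07 and 0.076. Six more rows match, but their changes are 0.02 points or less (main Nitrospirae; control Spirochaetes, Nitrospirae, Tenericutes, Caldithrix and Thermotogae), so they carry little information. The one exception of the 15 is main Tenericutes, with d = −0.05 and m = −0.095.

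**The other seven phyla.**

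| Group, phylum | d (points) | Printed CI | m | d inside? | d/100 inside? | log10 of mean ratio |
|---|---|---|---|---|---|---|
| Main Bacteroidetes | 2.89 | −0.01; 0.07 | 0.030 | no | yes | 0.041 |
| Main Firmicutes | −6.56 | −0.09; −0.02 | −0.055 | no | yes | −0.059 |
| Main Proteobacteria | 2.73 | 0.10; 0.28 | 0.190 | no | no | 0.152 |
| Main Actinobacteria | −1.15 | −0.15; 0.14 | −0.005 | no | yes | −0.116 |
| Main Euryarchaeota | −0.24 | −0.42; 0.10 | −0.160 | yes | yes | −0.075 |
| Main Verrucomicrobia | 0.46 | −0.09; 0.32 | 0.115 | no | yes | 0.192 |
| Main Cyanobacteria | −0.15 | −1.95; −0.17 | −1.060 | no | no | −0.287 |
| Control Bacteroidetes | 2.50 | −0.06; 0.08 | 0.010 | no | yes | 0.035 |
| Control Firmicutes | 0.40 | −0.06; 0.07 | 0.005 | no | yes | 0.004 |
| Control Proteobacteria | −0.26 | −0.10; 0.12 | 0.010 | no | yes | −0.015 |
| Control Actinobacteria | −3.56 | −0.46; −0.10 | −0.280 | no | no | −0.208 |
| Control Euryarchaeota | −0.48 | −0.74; 0.24 | −0.250 | yes | yes | −0.348 |
| Control Verrucomicrobia | −0.24 | −0.97; 0.85 | −0.060 | yes | yes | −0.057 |
| Control Cyanobacteria | 0.07 | −1.42; 1.89 | 0.235 | yes | yes | 0.081 |

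No midpoint equals d, and ten intervals exclude d. Rounding does not explain this. The closest case is main Cyanobacteria, where d is at most 0.16 in size while the near limit is at least 0.165. Using the changes quoted in the text for the main group gives the same six exclusions.

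**One scale for the whole table?**
- Fractions: three of the ten still fail (0.0273 against 0.10 to 0.28; −0.0015 against −1.95 to −0.17; −0.0356 against −0.46 to −0.10), and only two of the 14 midpoints match (main Bacteroidetes, control Firmicutes). Chloroflexi in both tables and Synergistetes would also fail.
- Log10: the log10 ratio of means lies inside all 14 intervals above. For main Chloroflexi, though, it is log10(0.23/0.07) = 0.517 against 0.04 to 0.28, and phyla with a 0.00% mean have no such ratio.

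**Do the p-values go with the intervals?** t = m / (half-width/2.045). Main Actinobacteria: −0.005/(0.145/2.045) = −0.07, p = 0.944 (printed 0.951). Control Actinobacteria: −0.28/(0.18/2.045) = −3.18, p = 0.0035 (printed 0.003). The 14 rows agree broadly; the loosest is control Euryarchaeota, 0.305 against 0.209. The tests were therefore apparently run on the unnamed scale.

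**Main Tenericutes.** The interval −0.2; 0.01 implies p of about 0.07, against 0.491 printed. An upper limit of 0.1 would give m = −0.05 and p of about 0.50, so this looks like a separate misprint.

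**The case against.** The best defence is a simple unit slip. Read as fractions, seven of the ten excluded changes fall inside their intervals, including main Firmicutes. That stands as far as it goes: for Firmicutes alone a slip cannot be ruled out. It does not explain main Proteobacteria, main Cyanobacteria or control Actinobacteria.

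A second defence is that transforming variable by variable is legitimate, and the antibody results do mention bringing variables to normality. That also stands, provided it is disclosed. The gut section discloses nothing.

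A reader might go further than the documents allow in four ways:
- **The second scale is log10.** It fits by containment, but midpoints match in only about three of 14 rows (both Firmicutes rows and control Verrucomicrobia), and a log of a ratio of means is not a mean of logs. A back-transformed fall in Proteobacteria of 21% to 48% (1 − 10^−0.10 to 1 − 10^−0.28) is an assumption.
- **The split is abundant against rare phyla.** Main Cyanobacteria, at 0.16%, is rarer than main Chloroflexi, at 0.23%.
- **Conclusions reverse.** Main Actinobacteria (quoted as a rise, tested change near zero) and control Proteobacteria (a rise beside an interval centred on a small fall) are null results, p = 0.951 and 0.823. The combined Bacteroidetes and Firmicutes claim rests on Tables 3 and 4.
- **Table 4 is faulty too.** It prints only p-values, and nothing shows a mixed scale there.

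**Conclusion.** The point holds as a fault in reporting and in the specification of the analysis. The interval column is unlabelled and not on one scale: seven phyla are off the percentage-point scale in both arms, and ten of 29 intervals exclude the change beside them. For four of the 14 rows (Euryarchaeota in both arms; Verrucomicrobia and Cyanobacteria in the control group) the evidence is only the off-centre midpoint.

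The count rests on the printed means and limits and on both readings being available for every patient, as the flow list indicates. It does not depend on what the second scale is, which the documents do not identify. The direction of the main-group Firmicutes and Proteobacteria changes agrees with the sign of their intervals. What is unreliable is the size of effect and precision that a reader would take from the tables.

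**What to change.** - In the gut microbiota section of the Statistical Analysis Plan, name any transformation used, the phyla it applies to and the rule for zero readings.
- Label the scale of every interval in Tables 1 and 2.
- For every phylum in both arms, give the mean change with its 95% CI in percentage points. Where a transformed scale was tested, add the back-transformed estimate and interval.
- Make the text quote the quantity that was tested, and reconcile it with Table 1: Firmicutes 7.62 in the text against 6.56 from the table, Actinobacteria 1.42 against 1.15, Bacteroidetes 3.03 against 2.89, Proteobacteria 2.83 against 2.73.
- Check the main Tenericutes row.
- State the scale used in Table 4, and re-run it only if it proves to mix scales.

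The cost is a re-run of existing data and relabelling, with no new data collection. Some nominal significances may change.

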1. Based on the results of gut microbiome sequencing, ELISA (antiphospholipid antibodies), and biochemical blood analysis in the main and control groups, we determine the dynamic changes of those parameters during COVID-19 rehabilitation.
2. According to the results, the effectiveness of Saumal itself regarding these 2 parameters will be evaluated.
3. Develop recommendations and an algorithm for patient management after COVID-19 to prevent complications.

Study Design

Study Type: Interventional

Primary Purpose: Treatment

Interventional Study Model: Parallel Assignment

Number of Arms: 2

Masking: None (Open Label)

Allocation: Randomized

Enrollment: **60 patients.** Originally, we planned to include 38 patients in the main group and 37 in the control group. Overall, these groups were evenly divided, with 30 patients in each group.

Arms and Interventions

Arms	Assigned Interventions
Experimental: Main Group Patients who had suffered from COVID-19 in the six months before the start of the study. Patients will receive Saumal (freeze-dried mare milk) for four weeks.	Dietary Supplement: Freeze-dried Mare Milk (Saumal) Freeze-dried Mare Milk (Saumal) is frequently reported for having therapeutic and dietary properties associated with specific chemical composition and certain physical properties of the product. It contains a total of about 40 biologically active components, the most important of them vitamins A, C, B1, B2, B6, and B12, amino acids, enzymes, and trace elements (low molecular weight peptides, lactalbumins, and globulins). Saumal will be administered to patients at a dose of 25 grams of dry powder per 200 ml of water, 2 times a day, 30 minutes before the meal, for 4 weeks.
No Intervention: Control Group Patients who had suffered from COVID-19 in the six months before the start of the study. There will be no intervention.	

Eligibility

Minimum Age: 18 Years

Maximum Age: 75 Years

Sex: All

Gender Based: No

Accepts Healthy Volunteers: No

Inclusion Criteria:

Age 18 years and older;

Patients in rehabilitation after COVID-19;

Signed informed consent;

Presence of patient's history of COVID-19, reliably established by PCR+ /presence of IgG/ diagnosis of coronavirus pneumonia on Computer Tomography based on discharge from hospital or outpatient records.

Exclusion Criteria:

Chronic inflammatory bowel disease;
Gut microbiota transplantation;
Chronic pancreatic disease, period of exacerbation;
Liver cirrhosis, Metavir stage 3-4;

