After bringing the variables to the normal distribution, the statistical significance was found in the control group only (Table 8).

Table 8. Statistical analysis of normally distributed antiphospholipid antibody levels.

	95% CI	p-value (t-student)
Main group, IgM	-0,03; 0,11	0,185
Main group, IgG	-0,07; 0,11	0,726
Control group, IgM	0,04; 0,14	0,001
Control group, IgG	0,05; 0,15	0,0001

ANOVA was performed to determine the direct effect of the natural food product on the aPL values (Table 9). ANOVA did not reveal any statistical significances.

Table 9. Finding the effect of the freeze-dried mare's milk on the antiphospholipid antibody values (ANOVA - analysis of variance).

Antibody name	p (One-way ANOVA)
IgM	0,541
IgG	0,938

aPL values in almost all patients of both groups were ranged normally. The intersection of all confidence intervals of medians and means indicates the absence of statistical significance between these indicators. The results before and after bringing the aPL values to normal distribution differ greatly, especially for the IgM level in the main group. One-factor analysis of variance also showed the lack of significance of the studied factor. These several theses can explain the given results. First, initial aPL values could have been normalized over 6-9 months after COVID-19. Second, there were screening kits in the study. Therefore, the obtained results do not show the levels of specific phospholipids (phosphatidylcholine, phosphatidylethanolamine, aCL, anti- β 2-GP1, etc.). Third, the severity of COVID-19 was not considered as an inclusion criterion.

Quality of life analysis.

The quality of life of post-COVID patients in the main group statistically significantly improved in both physical and mental health components after using mare's milk. In the control group, there was no statistically significant change in quality-of-life indicators for both physical and mental health components. Even though the average score for the physical component in the control group is higher than in the main group, the level of statistical significance and the confidence interval of both groups allow us to conclude that freeze-dried mare's milk can have a positive effect on this indicator of the quality of life of post-COVID patients (Table 10).

Table 10. The average quality-of-life score in patients of the main and control groups.

	Quality-of-life components							
	Physical				Mental			

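### Table 4, the only between-arm microbiome test, does not agree with Tables 1 and 2: Bacteroidetes conflicts on every scale that can be checked, and Firmicutes and Actinobacteria depend on an unstated scale

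*Combined protocol and SAP*

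**What the plan says.** The SAP's gut microbiota paragraph gives the between-arm method in one sentence: "A single-factor analysis of variance was employed to verify the effect of administering freeze-dried mare's milk, which could potentially affect the indicators of gut microbiota". It does not name the dependent variable or say whether percentages were transformed. The Results repeat the method above Table 4: "To determine the effect of freeze-dried mare's milk on the gut microbiota at the phylum level, a one-factor analysis of variance was performed". Table 4 then prints one p-value per row, for example "Bacteroidetes 0,180", without means, standard deviations, differences or degrees of freedom. From it the text names Firmicutes, Elusimicrobia and Proteobacteria as related to the milk.

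Tables 1 and 2 give within-arm paired results, such as "Bacteroidetes 32,32% 29,43% -0,01; 0,07 0,178" in the main group, "Bacteroidetes 32,27% 29,77% -0,06; 0,08 0,754" in the control group, and "Firmicutes 45,31% 51,87% -0,09; -0,02 0,001" in the main group. The text introducing Table 3 describes a difference between groups, but the table holds two within-arm Wilcoxon p-values (0.026 and 0.213). Table 4 is therefore the only comparison between arms. On numbers, Study Design states: "Overall, these groups were evenly divided, with 30 patients in each group".

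**The concern.** With two equal arms, a one-way ANOVA on change is a two-sample t-test, so its p-value follows from each arm's mean change and confidence interval. Table 4 can be checked against Tables 1 and 2, and several rows do not match. Bacteroidetes stands out because the two arms moved almost identically, yet its between-arm p is close to what a moderate difference would give.

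The randomised evidence that milk alters the microbiome rests on this table. Firmicutes is singled out in the conclusion, and its printed p of 0.048 lies just under 0.05. If the outcome or scale behind Table 4 differs from that behind Tables 1 and 2, the reader cannot tell, and the list of phyla attributed to milk could depend on that choice.

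**Working it through.** **Inputs.** 95% CIs for paired change (before minus after) from Tables 1 and 2; p-values from Table 4; 30 patients per arm, so t(0.975, 29) = 2.045 and 58 df between arms.

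**Formulas.** Mean change = CI midpoint. SE per arm = half-width / 2.045. SE of contrast = √(SE₁² + SE₂²). t = difference of midpoints / SE of contrast; F = t². Ranges move every CI limit by ±0.005.

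**Rows that reproduce within rounding.** Chloroflexi 0.228 (printed 0.220), Spirochaetes 0.319 (0.340), Nitrospirae 0.20 (0.143; range 0.09 to 0.39), Fusobacteria 0.132 (0.140), Elusimicrobia 0.040 (0.044). Elusimicrobia on final values would give 0.104, so change fits better there.

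**Rows that do not reproduce, although their CIs return their own paired p-values at n = 30 within rounding.**

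| Phylum | Difference | SE main | SE control | SE contrast | t | p (range) | Printed |
|---|---|---|---|---|---|---|---|
| Bacteroidetes | 0.03 − 0.01 = 0.02 | 0.0196 | 0.0342 | 0.0394 | 0.51 | 0.61 (0.45–0.80) | 0.180 |
| Firmicutes | −0.055 − 0.005 = −0.06 | 0.0171 | 0.0318 | 0.0361 | −1.66 | 0.10 (0.057–0.171) | 0.048 |
| Proteobacteria | 0.19 − 0.01 = 0.18 | 0.0440 | 0.0538 | 0.0695 | 2.59 | 0.012 (0.008–0.017) | 0.043 |
| Actinobacteria | −0.005 + 0.28 = 0.275 | 0.0709 | 0.0880 | 0.1130 | 2.43 | 0.018 (0.014–0.022) | 0.186 |

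**Bacteroidetes on raw percentages.** The falls are 32.32 − 29.43 = 2.89 and 32.27 − 29.77 = 2.50, a contrast of 0.39 points. Final values differ by 29.77 − 29.43 = 0.34. For p = 0.180, t = 1.357, so the SE must be 0.39/1.357 = 0.29 or 0.34/1.357 = 0.25. Dividing by √(2/30) gives an SD of 1.11 points (change) or 0.97 (final). If the main arm's paired p of 0.178 applies to its 2.89-point fall, the change SD is (2.89/1.380) × √30 = 11.5 points, about ten times larger. The text above Table 1 gives that fall as 3.03; the contrast is then 0.53 and the SD needed is still only 1.5.

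Table 4's own rows give a separate bound. Bacteroidetes is the sum row minus Firmicutes, so its SE cannot be below the gap between their two SEs. On raw change, Firmicutes implies 6.96/2.020 = 3.445 and the sum row (p = 0.037) implies 6.56/2.135 = 3.073. The gap is 0.373, so t is at most 0.39/0.373 = 1.05 and p at least 0.30 (0.25 after rounding). On final values p is at least 0.28 (0.23 after rounding).

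**Firmicutes and Actinobacteria on raw change.** Firmicutes at 0.048 needs an SD of 13.3 points, and Actinobacteria at 0.186 (contrast 2.41) needs 7.0. Both are plausible.

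**Rows that cannot be judged.** At n = 30 these CIs do not return their own paired p-values:
- Euryarchaeota control: 0.296 to 0.315 (printed 0.209).
- Verrucomicrobia: main 0.241 to 0.282 (0.223), control 0.885 to 0.903 (0.871).
- Cyanobacteria: main 0.021 to 0.022 (0.028), control 0.769 to 0.778 (0.728).

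Tenericutes gives 0.26 against 0.657, but its main-arm CI (−0.2 to 0.01) implies a paired p of 0.074 against the printed 0.491. An upper limit of 0.1 would give 0.50 for the paired p and 0.662 for Table 4.

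**Table 9 against Table 8, same method.** IgM 0.24 (0.16 to 0.35) against 0.541; IgG 0.12 (0.08 to 0.17) against 0.938.

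**The case against.** The strongest reply is that the model is assumed. The outcome and scale of the ANOVA are never stated, and some paired CIs are clearly not in percentage units: main-arm Proteobacteria falls 2.73 points (0.0273 as a fraction), while its CI runs from 0.10 to 0.28. The rows that reproduce have CIs centred at or close to the raw percentage-point change, which suggests that Table 4 may have used raw percentages throughout. This stands, and it limits several stronger readings that a reader might infer:

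- *That the Bacteroidetes p is impossible.* Transformed second-test values cannot be checked. As an assumed illustration, lognormal data with means 29.43 and 29.77 and log10 SDs of 0.10 and 0.28 give p = 0.179. A before-after coding within the main arm could also give 0.180 (SD about 8.2 points), but that would not compare the arms.
- *That 0.180 was carried over from Table 1's 0.178.* The values are close, but nothing in the document shows the cause.
- *That Firmicutes is not significant and Actinobacteria is.* This follows only if Table 4 used the scale of the printed CIs.
- *That eight rows are wrong.* Three cannot be tested at n = 30, and Tenericutes points to a misprinted limit in Table 1.
- *That Table 9 overturns something.* The text reports antibody results before and after transformation without saying which version Table 9 used. The main-arm IgM CI also misses its own paired p (0.199 to 0.315 against 0.185). The reported conclusion, "ANOVA did not reveal any statistical significances", is the same either way.

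The reply does not remove the Bacteroidetes conflict on the three outcomes that can be computed. If scale explains the other rows, then an undisclosed change of scale decides two significance calls.

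**Conclusion.** The inconsistency is real, in limited form. Assuming 30 patients per arm in each tested row, four of 13 phylum rows disagree with Tables 1 and 2 beyond rounding when read as change on the CI scale. Bacteroidetes (0.180) also disagrees with raw change and raw final values; only an outcome that cannot be checked could rescue it. Bacteroidetes is non-significant at either value, so that row signals a problem with the table and does not itself reverse a finding.

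The effect on the milk-related list is conditional. On the CI scale Firmicutes would leave it and Actinobacteria, which rose in controls, would become significant; on raw change neither is shown. Proteobacteria (0.012) and Elusimicrobia (0.040) remain below 0.05 on the CI scale. The combined Bacteroidetes and Firmicutes row (0.037) cannot be rebuilt on that scale because Table 3 gives no CI. The documents therefore do not show that the milk effect is absent. They show that its only between-arm test cannot be relied on until the model is stated and the rows are rechecked.

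**What to change.** Re-run every row of Table 4 from the existing data on one stated outcome and the same scale as Tables 1 and 2, and label that scale in all three tables. Give the n used in each row. Print the between-arm mean difference with its 95% CI and F beside each p. Recheck Table 9 against Table 8 in the same way. Correct Bacteroidetes, the Tenericutes CI in Table 1 and any other row that changes, then rewrite the statement above Table 4 on which phyla relate to the milk, and the conclusion below it, from the corrected table. Add the outcome and scale to the ANOVA sentences in the SAP.

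This needs no new data: the cost is one re-analysis and corrected tables. The downside for the sponsor is that the Firmicutes result may become less favourable.
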